Purpose and Objectives

Our hypothesis is: In carefully selected subjects with Stage A or B HF (i.e., subjects with elevated cardiac troponin T (hs-cTnT) and elevated 10-year HF risk), augmented therapy for 18 months with the aldosterone antagonist spiroloactone or the nonselective beta-blocker carvedilol will decrease hs-cTnT and be associated with improved cardiac and vascular function compared with subjects treated with usual care.

Our specific aim is to evaluate using a prospective randomized open label blinded end point evaluation (PROBE) study if subjects with stage A or B HF (i.e., individuals at risk for incident HF hospitalization), increased hs-cTnT levels (>5

ng/L), 10-year estimated HF risk >5% and a systolic BP between 120 mmHg and 155 mmHg who receive aggressive treatment with the addition of spironolactone or carvedilol have decreases in hs-cTnT and improved noninvasive measures of cardiovascular function (cardiac and vascular strain) compared with usual care.

Protocol Risks/Subjects

Risk Category

Category 3: Research involving greater than minimal risk and no prospect of direct benefit to the individual subject, but likely to yield generalizable knowledge about the subject's disorder or condition.

Subjects

Gender:

Both

Age:

Adult (18-64 yrs), Geriatric (65+ yrs)

Ethnicity:

All Ethnicities

Primary Language:

English

Groups to be recruited will include:

Asymptomatic patients with chronic conditions, healthy

Which if any of the following vulnerable populations will be recruited as subjects?

Vulnerable populations require special protections. How will you obtain informed consent, protect subject confidentiality, and prevent undue coercion?

Pregnant woman/fetus

Will pregnant women and/or fetuses (as described in 45 CFR 46 Subpart B) be enrolled in the research?

No

Neonates

Will neonates of uncertain viability or nonviable neonates (as described in 45 CFR 46 Subpart B) be enrolled in the research?

No

Children

Will children be enrolled in the research?

No

Design/Procedure

Design

Select one category that most adequately describes your research:

u) Drug, Phase II, Single Center

Discuss the research design including but not limited to such issues as: probability of group assignment, potential for subject to be randomized to placebo group, use of control subjects, etc.

We will use a prospective open label blinded end point (PROBE) design to allow us to conduct our proposed study.

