Only veterans will be enrolled in this study. Eligible subjects will be recruited from primary care and cardiology clinics at the MEDVAMC and will include patients in Stage A or B HF whose risk factors (which led to their classification as Stage A/B) are adequately controlled and who have an hs-cTnT level greater than 5 ng/L and estimated 10 year HF risk greater than 5%.

Eligible individuals will be randomized (equal numbers in each group) to spironolactone, carvedilol or usual care.

Randomization will be performed by the research pharmacy at MEDVAMC supported by the Institution For Clinical and Translational research (ICTR) at Baylor College of Medicine using deidentified data.

Subjects who qualify will have hs-cTnT measured using a novel high sensitivity assay along with NT-proBNP. Those with cTnT greater than 5 ng/L and an estimated 10-year HF risk greater than 5%, estimated based on a lab result based model will be eligible to continue in the study and will then have an echocardiogram, carotid ultrasound imaging, and arterial stiffness assessment (pulse wave velocity). The echocardiogram will be interpreted to ensure that there are no clinically significant abnormalities that should be addressed by the subjects physician or that would exclude the subject from the study.

The PI will review the images to ensure that they are of adequate quality to allow the measurement of cardiac strain (the primary end point). Those who meet all the inclusion criteria will then proceed to randomization.

RATIONALE FOR CHOICE OF STUDY POPULATION:

Our goal was to choose a population who were at higher risk among individuals with Stage A/B HF so that preventive therapies, if successful, would have a favorable risk vs. benefit ratio. Three important inclusion criteria were considered in the choice of our study population:

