1. Systolic BP: We chose a systolic BP category (120 to 155 mm Hg) for many reasons. First, epidemiological data suggest that systolic BP in this range is associated with increased risk, yet studies that have targeted lower BP have not shown benefit. In a recent study describing the current epidemiology of heart failure with preserved left ventricular function (HFpEF), almost 75% of individuals with HFpEF had systolic BP between 110 and 160 mm Hg, and ~55% had systolic BP between 120 and 159 mmHg. Treating patients with systolic BP <120 mm Hg or withholding treatment from those with systolic BP greater than 150 mm Hg will be unethical, and hence we opted for the systolic BP range of 120 to 155 mm Hg.

2. Troponin T value: As we have shown in the ARIC study, hs-cTnT values (especially greater than 5 ng/L) have been associated with significantly increased risk for HF, even after adjusting for age, race, systolic BP, antihypertensive medication use, current smoking, former smoking, diabetes, BMI, prevalent CHD, heart rate (ARIC HF Model) and log NT-proBNP. In the ARIC population aged 55 to 75 years, 60% of the men and 27% of the women had hs-cTnT greater than 5 ng/L. Furthermore, for hs-cTnT values less than 5 ng/L, the reliability of the assay is lower. Therefore, an hs-cTnT value of greater than 5 ng/L seems to be an appropriate cut point for our study.

3. Estimated HF risk: We have also shown in the ARIC study that using a risk model that includes age, race, hs-cTnT, and NT-proBNP, ~61% of men and ~46.5% of women had an estimated 10-year risk of HF greater than 5%, and ~35% men and 20% women had a risk greater than 10%. The inclusion criteria as listed, by requiring both hs-cTnT and estimated HF risk cut points, will result in a more selective group (rather than all Stage A/B HF) in whom the risk vs. benefit profile should be more favorable.

Inclusion Criteria:

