Data on change in strain with various medications are limited. However, a 1 to 1.5% absolute difference in longitudinal strain has been associated with outcomes. Therefore, assuming a conservative standard deviation of 3% (as described in studies), an alpha of 0.05, and a power of 0.8, we would require approximately 62 subjects per group.

Therefore, a sample size of 205-210 subjects should be a reasonable estimate (accounting for an approximately 10% drop-out rate)

Data Analysis

Provide a description of your plan for data analysis. State the types of comparisons you plan (e.g. comparison of means, comparison of proportions, regressions, analysis of variance).

Which is the PRIMARY comparison/analysis? How will the analyses proposed relate to the primary purposes of your study?

Primary analysis: To better inform the analyses planned, descriptive statistics (means and standard deviations of continuous variables and frequency of discrete variables) of subjects demographic characteristics and echocardiogram, vascular ultrasound, and biomarker variables will be computed at each measurement time and compared among the usual care and two drug treatment groups. All analyses will be conducted using the intention-to treat(ITT) principle. Statistical tests with a 2-sided P-value less than 0.05 will be considered statistically significant. When multiple comparisons are involved, Bonferroni correction for the type I error will be applied. Each continuous primary and secondary outcome will first be examined for its normality using the Shapiro Wilk test. When normality is verified, an analysis of variance (ANOVA) approach will be used to compare the mean change among the usual care and two drug treatment groups. Pairwise comparisons between the usual care and each of the drug groups will also be performed using the least significant difference method under the ANOVA framework. When the normality assumption is violated, the Kruskal Wallis nonparametric test will be applied.

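### If Shapiro-Wilk rejects normality, the primary analysis names only a three-group Kruskal-Wallis test, with no drug-versus-usual-care test or effect estimate

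*Combined protocol and SAP*

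**What the plan says.** In the Data Analysis section (Primary analysis), every continuous primary and secondary outcome "will first be examined for its normality using the Shapiro Wilk test". If it passes, mean change is compared across the three groups by ANOVA. Usual care is then compared with each drug, these contrasts being "performed using the least significant difference method under the ANOVA framework". If it fails, "When the normality assumption is violated, the Kruskal Wallis nonparametric test will be applied". Nothing further is said about that branch. A general sentence applies Bonferroni correction where there are multiple comparisons.

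The section gives no significance level for the normality test. It does not say whether the test is applied to pooled data, to each arm or to residuals, or whether hs-cTnT is analysed raw or logged.

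Under Purpose and Objectives, the hypothesis is that spironolactone or carvedilol "will decrease hs-cTnT and be associated with improved cardiac and vascular function compared with subjects treated with usual care". The Design section identifies cardiac strain as the primary end point. The Secondary Analysis paragraph adds a longitudinal model with a time-by-group term for each primary and secondary end point, with and without baseline covariates.

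**The concern.** The trial asks two questions: does each drug do better than usual care? A three-group omnibus rank test asks whether the three distributions differ anywhere. It names no arm, gives no effect size, and can be significant because the two drugs differ from each other. If the normality test rejects, the prespecified primary analysis stops there. Pairwise tests, their alpha and any estimate would have to be chosen after the data are seen, in an open-label trial.

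The gate also makes the analysis of strain depend on a preliminary test. Even exactly normal data fail it about 5% of the time, and the primary comparison then moves from a difference in means to a comparison of ranks.

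**Working it through.** **1. The plan's sample size is for a pairwise comparison.** Inputs from the Sample Size section: difference 1 to 1.5, SD 3, and "an alpha of 0.05, and a power of 0.8, we would require approximately 62 subjects per group". The Data Analysis section makes tests two-sided.

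n = 2(1.960 + 0.842)² × 3² / 1.5² = 2 × 7.85 × 4 = 62.8 per group.

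This agrees with the plan's 62 (a difference of 1.0 would need 142). The total is 3 × 62 = 186, and 186/0.9 = 207, inside the stated 205-210. The formula is for two groups, so the trial was sized for the comparison that the non-normal branch omits.

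**2. What each branch specifies.**

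| | Normality accepted | Normality rejected |
|---|---|---|
| Three-group test | ANOVA on change | Kruskal-Wallis |
| Each drug vs usual care | Least significant difference | None named |
| Effect estimate | Mean change | None named |
| Confidence interval | Not stated | Not stated |
| Baseline as covariate | No | No |

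The Bonferroni sentence adjusts comparisons; it does not create them.

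**3. What the omnibus test leaves open.** Simulation with 62 per arm, normal strain change with SD 3, and 0.05/2 = 0.025 for each contrast with usual care:

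- One drug better by 1.5, the other null: Kruskal-Wallis rejects in about 80% of trials. In about 12-14% of all trials it rejects while neither rank-sum test against usual care reaches 0.025.
- Drugs at +0.75 and -0.75 from usual care: it rejects in about 66%, and in about 32% of all trials neither contrast reaches 0.025.

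**4. How often the gate trips for hs-cTnT.** The documents give no hs-cTnT distribution. I assumed lognormal values, median 9 ng/L before the entry cut at 5 ng/L, log-scale baseline-to-follow-up correlation 0.7 to 0.95, and Shapiro-Wilk at 0.05.

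| Log-SD | Raw change rejected |
|---|---|
| 0.3 | 41-56% |
| 0.4 | 69-77% |
| 0.6 | 95-99.5% |

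The ranges cover pooled residuals and separate tests by arm; pooled over 1,500 trials per scenario they run from 41 to 98%. On the log scale rejection is about 4-7%. The unstated scale therefore largely decides the branch.

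**5. What a baseline-adjusted contrast gains for strain.** Take the plan's SD of 3 as the SD of change and let ρ be the baseline-to-final correlation (assumed). The variance of the adjusted contrast relative to change is (1 + ρ)/2, so the effective SD is 3√0.75 = 2.60 at ρ = 0.5 and 3√0.85 = 2.77 at ρ = 0.7. For normal data the rank-sum test has relative efficiency 3/π = 0.955, an effective SD of 3.07. Power = Φ(1.5 / (SD × √(2/62)) − z):

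| Analysis, 62 per arm, difference 1.5 | alpha 0.05 | alpha 0.025 |
|---|---|---|
| Rank-sum on change | 0.78 | 0.68 |
| t-test on change | 0.79 | 0.71 |
| Adjusted for baseline, ρ = 0.7 | 0.85 | 0.78 |
| Adjusted for baseline, ρ = 0.5 | 0.89 | 0.83 |

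Simulation gives 0.77, 0.85 and 0.89 at alpha 0.05 for the rank-sum and the two adjusted contrasts (0.67, 0.77 and 0.82 at 0.025).

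**6. Where the gain for hs-cTnT comes from.** Same assumptions as step 4, one active drug, alpha 0.05, 1,500 trials per row:

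| Log-SD, ρ, reduction | t, raw change | Rank, raw change | t, log change | Log scale with baseline |
|---|---|---|---|---|
| 0.4, 0.7, 10% | 0.38 | 0.40 | 0.46 | 0.50 |
| 0.6, 0.7, 15% | 0.39 | 0.42 | 0.52 | 0.56 |
| 0.6, 0.85, 15% | 0.62 | 0.70 | 0.80 | 0.81 |

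Over 12 scenarios (log-SD 0.3 to 0.6, ρ 0.7 or 0.85, reduction 10 or 15%), the last column exceeds the raw-change analyses by about 7 to 19 points where raw-change power is below 0.9, and by 0 to 4 points above that. Ranks do not lose to the raw t-test. The gain comes from the log scale and the baseline covariate.

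**The case against.** The strongest reply is that the plan answers the question elsewhere. The secondary longitudinal model covers every primary and secondary end point, does not depend on the normality test, and can include baseline covariates. The visit list in the Procedure section places imaging at randomization and the final visit. With two time points, the time-by-group term is essentially the difference in mean change. That stands, and it rules out saying that the trial cannot answer its question. But the model is labelled secondary, mentions no log scale, and names neither a drug-versus-usual-care contrast nor an interval. It limits the damage without filling the gap in the primary analysis.

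A reader might also infer that hs-cTnT is bound to fail the gate. The documents do not support this. They give no spread and no scale, and the entry cut acts on baseline rather than on change. The mention of "prevalent CHD, heart rate (ARIC HF Model) and log NT-proBNP" describes covariates in a cohort analysis, not this trial's analysis scale.

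Nor is it right that the non-normal branch discards baseline or that ranks cost power. The plan's stated outcome is change, which uses baseline, and the missing covariate is common to both branches. Step 6 shows no power penalty for ranks against the raw t-test. Removing the gate while keeping ANOVA on raw change would not recover the power.

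Finally, a statistician would probably add pairwise rank tests unprompted. That is likely, but the method and alpha would then not be prespecified.

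**Conclusion.** The point holds for the primary analysis as written: when normality is rejected, it contains no drug-versus-usual-care test or effect estimate. This rests on the text alone. For hs-cTnT the branch is likely to be reached on the raw scale and unlikely on the log scale; the percentages depend on the assumed median, spread and correlation. For strain, how often it is reached depends on a distribution the documents do not give.

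The strain gain, from about 0.77-0.79 to 0.85-0.89 at alpha 0.05, assumes a correlation of 0.7 to 0.5 and that the plan's SD of 3 describes change. It is a benefit of baseline adjustment, not a loss caused by the gate. Inflation of type I error is not part of this point. The change should be made, but the flaw does not invalidate the trial.

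**What to change.** Remove the normality test as a rule for choosing the analysis, and prespecify:

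- **Strain:** a linear model of the 18-month value on arm, baseline value and the stratification factors (age, CHD, ACE-inhibitor/ARB use, hs-cTnT above 14 ng/L). Name two contrasts, each drug against usual care, with estimates and confidence intervals. Apply the plan's Bonferroni correction explicitly: 0.05/2 = 0.025 each, with matching 97.5% intervals.
- **hs-cTnT and NT-proBNP:** the same model on the log scale, with baseline also logged, reported as ratios of geometric means.
- **Sensitivity:** rank tests, including the two pairwise tests against usual care.

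The form in which age enters the model should be stated, since the plan gives no cut point for stratification. The cost is analysis-plan wording. Baseline values and stratification factors are already collected, so no new data, visits or subjects are needed.

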Secondary Analysis: For each of the primary and secondary end points, the longitudinal mixed-effect model will be applied to compare the slope differences among the usual care and two drug treatment groups with and without adjusting baseline covariates. The main model can be described as mean outcome at time $t = b_0 + b_1*t + b_2*group + b_3*t*group$. The within-subject correlation structure will be assumed to follow spatial power correlation structure because of its uneven observational time intervals. The generalized estimation equation method will be used to perform the analysis. Secondary, exploratory analyses will be performed to evaluate prespecified subgroups; we will test changes in cardiac and carotid strain in responders (e.g., those whose cTnT levels stayed stable or decreased, those whose hs-cTnT levels were greater than 14 ng/L at baseline, those whose estimated HF risk was greater than 10%) in comparison with nonresponders.

Potential Risks/Discomforts

Potential Risks/Discomforts

Describe and assess any potential risks/discomforts; (physical, psychological, social, legal, or other) and assess the likelihood and seriousness of such risks:

1. Medications: Carvedilol and spironolactone are clinically used, generally well tolerated with limited side effects. Both medications lower blood pressure which will be closely monitored. Spironolactone can lead to hyperkalemia (increased potassium levels) and at higher doses can cause gynecomastia (mostly reversible). However we are excluding individuals with renal insufficiency and using lower dose spironolactone which will decrease the risk of these occurrences. Furthermore for those on spironolactone we will check their potassium levels after starting the medication and during each study visit. With carvedilol other than lower blood pressures and possibly a slower heart rate no other significant side effects are anticipated. Idiosyncratic reactions such as allergies to medications etc. are possible

2. As with any clinical study despite our best efforts, loss of confidentiality is possible

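### The secondary longitudinal model lets the randomised arms differ at baseline, so its slope test is in effect an unadjusted change-score comparison and less precise than a baseline-adjusted analysis

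*Combined protocol and SAP*

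**What the plan says.** Under Data Analysis, Secondary Analysis, the plan states for every primary and secondary end point that "the longitudinal mixed-effect model will be applied to compare the slope differences among the usual care and two drug treatment groups", and it does this "with and without adjusting baseline covariates". The covariates are not named. The mean model is "b_0 + b_1*t + b_2*group + b_3*t*group". On correlation it says "The within-subject correlation structure will be assumed to follow spatial power correlation structure", and on fitting, "The generalized estimation equation method will be used to perform the analysis". No random effects are written.

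Under Data Analysis, Primary analysis, an "analysis of variance (ANOVA) approach will be used to compare the mean change among the usual care and two drug treatment groups", with no baseline covariate. The same paragraph says "All analyses will be conducted using the intention-to treat(ITT) principle". The Sample Size section expects about 10% dropout. No method for missing data is given.

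The Design section randomises equal numbers to three arms and names cardiac strain as the primary end point. In the Procedure section, imaging is done at the randomisation visit and is listed again only for Visit 5. The usual-care paragraph of the same section can be read as imaging at 6 and 12 months as well.

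**The concern.** At t = 0 the model reduces to `b_0 + b_2*group`, so `b_2` is a free difference between arms before treatment starts. Randomisation makes that difference zero in expectation, and the model does not use this. Each subject's baseline is subtracted from the later value with weight one, whatever the correlation between the two. A baseline-adjusted analysis uses the weight that the data support and so has a smaller variance.

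For strain under the Visit 5 schedule, the longitudinal model therefore repeats the contrast of the change ANOVA and adds no precision. What is at stake is efficiency from data already being collected, not bias.

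A second, separate matter is the estimator. A mixed-effect model fitted by likelihood and a GEE fit are different procedures with different missing-data conditions. Two analysts could follow the paragraph and fit different models.

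**Working it through.** **Inputs.** Difference 1.5% (upper end of the stated 1 to 1.5%), SD 3%, alpha 0.05, power 0.8 and 62 per group come from Sample Size. Two-sided testing comes from Data Analysis. The correlation rho between baseline and 18 months is not in the documents, so I show 0.3 to 0.9. The text does not say whether 3% is the SD of change or of a single measurement, so both are shown.

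**The plan's own figure.** n = 2 × SD² × (1.96 + 0.84)² / difference² = 2 × 9 × 7.84 / 2.25 = 62.7, or 63 per group (64 with the t distribution), in line with the stated 62. Then 3 × 62 = 186; 186/0.9 = 207 and 186 × 1.1 = 205, both within the stated 205-210. A difference of 1% would need 142 per group.

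**What `b_3` estimates.** With two visits and a free intercept and slope per arm, the model is saturated in the means. So `b_3` times follow-up equals the difference in mean change. In 600 simulated two-visit trials (rho 0.6), the GEE estimate and the change-score estimate agreed to rounding error (1e-15).

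**Variance.** Take variance σ² at both visits.
- As written: 2σ²(1 − rho).
- Common baseline mean, or ANCOVA: σ²(1 − rho²).
- Ratio, common over as written: (1 + rho)/2.

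The simulation gave 0.196 against 0.248, a ratio of 0.79 against 0.80 in theory; ANCOVA also gave 0.196. Fitting the common-baseline model by the same GEE method recovered the precision.

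**More visits.** With three or four visits under spatial power correlation, the slope test keeps almost exactly the change-score variance. As written over common, the ratio is about 1.56, 1.34, 1.18 and 1.05 at rho 0.3, 0.5, 0.7 and 0.9, against 1.54, 1.33, 1.18 and 1.05 with two visits. Either reading of the imaging schedule leads to the same conclusion.

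**Baseline covariates.** A time-fixed covariate entered as a main effect shifts both visits equally and cancels from the slope. Adding baseline this way left `b_3` unchanged. Adding baseline and baseline-by-time made `b_3` equal the ANCOVA estimate (0.3474 for both in one simulated data set, against 0.3064 for the change score).

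**Power of this analysis**, difference 1.5%, 62 per arm, two-sided t test at 0.05, noncentrality 1.5/(SD × √(2/62)):

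| rho | (1+rho)/2 | 3% is SD of change: effective SD, power | 3% is SD of one measurement: effective SD, power |
|---|---|---|---|
| 0.3 | 0.65 | 3.00 → 2.42, 79% → 93% | 3.55 → 2.86, 65% → 83% |
| 0.5 | 0.75 | 3.00 → 2.60, 79% → 89% | 3.00 → 2.60, 79% → 89% |
| 0.7 | 0.85 | 3.00 → 2.77, 79% → 85% | 2.32 → 2.14, 95% → 97% |
| 0.9 | 0.95 | 3.00 → 2.92, 79% → 81% | 1.34 → 1.31, about 100% for both |

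The effective SDs are 3 and 3√((1+rho)/2) in the third column, and 3√(2(1−rho)) and 3√(1−rho²) in the fourth.

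**The case against.** The best defence is that this is a secondary analysis, that its estimate is unbiased, and that it is as precise as the planned primary ANOVA. All of that stands. Less precise here means less precise than ANCOVA or a common-baseline model. The gain is also small where rho is high: about 5% of variance at 0.9, with no material power gain if 3% is a single-measurement SD.

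The plan also runs the model with baseline covariates. That answers the point only if the covariates include the baseline outcome and its interaction with time. None is named and no interaction is stated.

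A reader might infer four stronger things that the documents do not support.
- *That the model throws the baseline away.* It does not: baseline enters as a response and is subtracted. What goes unused is the equality of baseline means under randomisation.
- *That baseline cannot also be a covariate because it is already an outcome.* It can, through a baseline-by-time term, as shown above.
- *That GEE causes the loss, or makes the result biased.* The free `b_2` causes the loss. Unweighted GEE in general needs dropout unrelated to outcome, but no material bias has been shown here. In a two-visit simulation with about 8.5% dropout that depended on baseline and differed by arm, GEE bias was at most about 0.006 strain points, against 0.09 to 0.21 for a complete-case change comparison. Nor does a GEE fit contradict the ITT statement.
- *That correcting this paragraph raises the power of the trial's primary test.* It does not. The primary test is the change ANOVA.

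**Conclusion.** The point holds as one of efficiency and clarity, not validity. The secondary slope test is in effect an unadjusted change-score test. Against a common-baseline or ANCOVA analysis it gives up a share of variance equal to (1 − rho)/2, that is 35%, 25%, 15% or 5% at rho 0.3, 0.5, 0.7 or 0.9. The power figures rest on three assumptions: rho, which the documents do not give; equal variance at both visits; and the meaning of the 3% SD. They describe this secondary analysis only, at a difference of 1.5% and alpha 0.05. The gain is worth having because it needs no extra subjects or measurements.

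The conflict between the mixed-effect label and GEE fitting is real but separate. It leaves the estimator and the missing-data assumption unclear where about 10% dropout is expected.

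**What to change.** 1. In Secondary Analysis, remove `b_2` so that all arms share one baseline mean, or use ANCOVA of the 18-month value with the baseline value as covariate.
2. Replace the single group term with a separate term for each drug against usual care, and report the estimated 18-month difference for each.
3. Name the covariates: the four stratification factors in the Procedure section (age, CHD, ACE-inhibitor/ARB use, hs-cTnT above 14 ng/L). For the hs-cTnT end point, ANCOVA is the simpler form, because one of these factors is a cut of its own baseline value.
4. Make the same baseline adjustment in the Primary analysis paragraph. Without this, the power of the primary test does not change.
5. State one estimator. A likelihood (REML) fit is preferable because it allows dropout to depend on observed values; keep GEE as a sensitivity analysis with its missing-data assumption stated.
6. Reconcile the usual-care paragraph with the Visit 3 to 5 descriptions on whether imaging is done at 6 and 12 months.

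The cost is a few sentences in the analysis plan, with no new data, visits or subjects.

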Baseline labs including a comprehensive metabolic panel, lipid panel, and hemoglobin A1C will be assessed (unless labs within 3 months are available). Additional blood will be stored for future biomarker analysis. These blood samples will be stored in the Research commons freezer or the Winters Center freezers located in building 110 at the MEDVAMC. The biomarker analyses to be performed will be based on additional funding that will be obtained as the current grant that supports this study will not have adequate funds to run additional biomarkers. Hence while related to the study in that all the data from this study will be used, the funding is to be obtained in the future and the biomarkers to be decided in the future. Blood from only those who meet the troponin inclusion criteria and who are ultimately randomized to this study will be stored. The others will be discarded.

Randomization visit and titration of medications: After the pre-randomization visit, those individuals who meet the inclusion criteria including hs-cTnT levels, HF risk score will come for the randomization visit. A history (medical, surgical, social, family and medication history and review of systems) and physical examination will be performed, and the findings will be documented on the case report form. The physical examination

would include BP measurements (3 taken 2 minutes apart). Orthostatic BP measurements will be performed as well. We will use calibrated BP machines in the clinic for the purpose of the study. They will have a 2D and 3D echocardiogram with Doppler. Those with adequate images for cardiac strain assessment will then be randomized to one of the 3 groups. Randomization will be achieved with the help of the research pharmacy and ICTR (institute for clinical and translational research). Randomization will be stratified for age, presence of CHD, ACE-inhibitor/ARB use, and hs-cTnT levels greater than 14 ng/L. In addition to an echocardiogram, a carotid ultrasound and a pulse wave velocity assessment will be performed at the randomization visit

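### The exploratory responder analysis mixes one post-randomisation group with two baseline groups and compares them with nonresponders, so as written it estimates no treatment effect.

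*Combined protocol and SAP*

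**What the plan says.** The combined protocol and SAP, Data Analysis, Secondary Analysis, introduces this work with "Secondary, exploratory analyses will be performed to evaluate prespecified subgroups". It continues: "we will test changes in cardiac and carotid strain in responders (e.g., those whose cTnT levels stayed stable or decreased". Two further examples of responders follow: "those whose hs-cTnT levels were greater than 14 ng/L at baseline", and subjects with estimated HF risk above 10%. All are to be tested "in comparison with nonresponders".

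Four other places bear on this:

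- **Purpose and Objectives** hypothesises that study therapy "will decrease hs-cTnT and be associated with improved cardiac and vascular function compared with subjects treated with usual care". hs-cTnT change is therefore an expected effect of treatment.
- **Randomization visit and titration of medications** states "Randomization will be stratified for age, presence of CHD, ACE-inhibitor/ARB use, and hs-cTnT levels greater than 14 ng/L". **Inclusion Criteria** makes an HF risk above 5% a condition of entry. Both traits are thus known before allocation. For HF risk this is an inference, since the sentence attaches the word baseline only to the 14 ng/L item.
- **Data Analysis, Primary analysis** applies intention to treat to all analyses and adds "When multiple comparisons are involved, Bonferroni correction for the type I error will be applied". The randomised comparison (ANOVA on mean change, each drug against usual care) is specified there separately.
- The **mixed model** in Secondary Analysis has terms for time, group and time-by-group. It has no subgroup or treatment-by-subgroup term.

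**The concern.** A subgroup analysis in a randomised trial should say whether the effect of treatment differs between kinds of patient. The planned contrast sets one kind of patient against another, and randomisation does not protect it.

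For the hs-cTnT-change group, anything that moves hs-cTnT and strain together within a patient will separate responders from nonresponders, whether or not a drug works. Because the trial's hypothesis couples falling hs-cTnT with better cardiac function, such a difference would be easy to read as support for it. It cannot show that lowering hs-cTnT with a drug improves strain.

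For the two baseline groups, *responder* is a misnomer. Setting high-risk against low-risk subjects measures prognosis. Whether each drug works differently at higher baseline hs-cTnT or HF risk is the question these groups could address, and no planned analysis addresses it.

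A lesser point is that *stable* has no margin and no visit is named for the hs-cTnT change.

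**Working it through.** **Inputs from the documents.** SD of strain 3%, strain difference 1 to 1.5%, two-sided alpha 0.05, power 0.8, about 62 per group, 205-210 in total with about 10% drop-out (Sample Size; alpha sidedness from Data Analysis); equal allocation to three arms.

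**The plan's own figure.** n per group = 2 × [3 × (1.960 + 0.842) / 1.5]² = 62.8, in line with 62. Three arms give 3 × 62 = 186 completers, and 186 / 0.9 = 207, inside 205-210. The stated size rests on the 1.5-point end of the range; 1 point would need 142 per group.

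**Assumed, because the documents are silent.** The correlation r between hs-cTnT fall and strain improvement (0 to 0.3), the share of responders p, and pooling of arms.

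**1. hs-cTnT-change group, neither drug affecting either variable.** Under bivariate normality with z = Φ⁻¹(p), the expected responder-minus-nonresponder difference is 3r × [φ(z)/p + φ(z)/(1−p)].

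- p = 0.5: 3r × (0.399/0.5 + 0.399/0.5) = 4.79r
- p = 0.8: 3r × (0.280/0.8 + 0.280/0.2) = 5.25r

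Rejection rates use a two-sided t-test with SD 3 and group sizes 186p and 186(1−p).

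| r | Difference, p = 0.5 | Rejection at 0.05 | Rejection at 0.05/3 | Difference, p = 0.8 | Rejection at 0.05 |
|---|---|---|---|---|---|
| 0 | 0 | 5% | 2% | 0 | 5% |
| 0.1 | 0.48 | 19% | 10% | 0.53 | 16% |
| 0.2 | 0.96 | 58% | 41% | 1.05 | 47% |
| 0.3 | 1.44 | 90% | 80% | 1.57 | 81% |

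The 0.05/3 column applies Bonferroni over the three definitions. Simulation of 20,000 trials agrees (p = 0.5: 4.9%, 19.2%, 58.1%, 91.3%). In a separate simulation of the same situation, the comparison of drug with usual care stayed near 5% throughout.

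**2. Baseline-trait groups.** Simulated with an assumed 30% share, SD 3 and 62 per arm:

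- both drugs improve strain by 1.5 points in everyone: the contrast averages about 0 and is significant in 5% of trials;
- no drug effect, but a 1.5-point prognostic difference between the groups: the contrast is 1.5 points and significant in 87%.

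**3. The alternative reading, arms compared within hs-cTnT responders.** Let the drug lower hs-cTnT by d SD without touching strain, a responder being a subject with hs-cTnT change ≤ 0. Drug minus usual care = 3r × [φ(d)/Φ(d) − φ(0)/Φ(0)].

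- d = 0: zero bias, about 5% false positives
- d = 0.5: 3r × (0.509 − 0.798) = −0.17 (r = 0.2), −0.26 (r = 0.3)
- d = 0.8: 3r × (0.368 − 0.798) = −0.26 (r = 0.2), −0.39 (r = 0.3)

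Expected responders are 62 × 0.5 = 31 on usual care and 62 × 0.69 to 62 × 0.79, or 43 to 49, on drug. Rejection is about 6-9%, and the bias runs against the drug.

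**4. Power of a proper interaction test, one drug against usual care.** With 62 per arm split 31/31, SE = 3 × √(4/31) = 1.08. Power for a 1.5-point difference in effect is Φ(1.5/1.08 − 1.96) = 0.285, and 80% power needs 2.80 × 1.08 = about 3.0 points. With a subgroup share of 30% or 20%, power falls to about 25% or 20%.

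**The case against.** The sentence is short, its groups are introduced as examples, and it is labelled exploratory. It follows text that compares outcomes among the three arms, so the authors may have meant to compare arms within each subgroup. On that reading the bias is modest, and an inert drug is falsely declared effective at no more than the nominal rate. On the pooled reading, the 58% and 90% are the power of an association test at a correlation the documents do not give, and at r = 0 the rate is the nominal 5%. Relating biomarker change to strain change is also a legitimate mechanistic question. An interaction test would have little power here, and reporting two drugs, two traits, two levels and two strain outcomes makes 2 × 2 × 2 × 2 = 16 small contrasts.

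Much of this stands and limits the weight of the point. The large percentages are not an error rate of the trial. The missing visit is minor: follow-up imaging is planned only at the final visit, which is the natural match for hs-cTnT, although 12 months remains possible.

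What does not stand is the appeal to intent. The text names responders and nonresponders and no arm. Adding arms would repair the two baseline groups, but the hs-cTnT-change group would still be selected on a post-randomisation outcome. Neither intention to treat nor Bonferroni turns the stated contrast into a randomised one.

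**Conclusion.** The concern holds. Carried out as written, the analysis estimates no treatment effect for any of its three example groups. Step 2 shows that, for a baseline trait, the contrast can be null when both drugs work in everyone and significant when neither does. For the hs-cTnT-change group, the difference expected with inert drugs reaches 0.96 to 1.44 points at assumed correlations of 0.2 to 0.3 and an even split. That is about the size the plan cites as associated with outcomes. It shrinks to nothing at r = 0, and these figures rest on normality and pooled arms.

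The primary arm comparison and the slope comparison by arm are untouched, and the analysis is labelled exploratory. The sponsor should correct this, but it does not threaten the trial's main inference.

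**What to change.** For baseline hs-cTnT above 14 ng/L and HF risk above 10%:

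- drop the word responder;
- report each drug against usual care, with confidence intervals, within each level of the trait;
- add a treatment-by-subgroup term to the ANOVA, or the corresponding time-by-group-by-subgroup term to the mixed model. The Kruskal-Wallis fallback has no such term, so the plan should name the model to be used if normality fails;
- keep the analysis exploratory and state its low power.

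Remove hs-cTnT change from the subgroup list. If it is kept, name the visit and report the association between strain change and hs-cTnT change, adjusted for arm and baseline values and labelled non-causal. Using hs-cTnT change as a continuous variable also removes the need to define *stable*.

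The cost is SAP wording and one added model term. No new data are needed, and the 14 ng/L cut is already a stratification factor. The downside is an imprecise result: 80% power for a 1.5-point interaction would take about 252 per arm with an even split, and about 300 or 393 if the subgroup share were 30% or 20%.
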